Within the multidisciplinary team, we have observed for several years the appearance of skin lesions similar to bedsores at the junction of the peripheral venous catheter and the extension tube. A practice has spontaneously developed within the department of placing a compress under this junction. The aim is to minimise physical or emotional distress and pain. Pain is a priority in the care of children and adolescents. Pain that is denied or unidentified and not relieved is remembered by the child, which can have consequences on their perception of pain and their subsequent acceptance of care.

To date, through our reading and research, we have found articles mentioning the risk of pressure sores in children associated with medical devices. However, little information is available on pressure sores associated with catheters, particularly on this specific technique for preventing lesions at the catheter-extension junction.

The aim of this study is therefore to compare two peripheral venous catheter fixation devices, with and without compresses, and to analyse the frequency of pressure ulcer occurrence and the severity of this injury.

1. JUSTIFICATION FOR THE STUDY

1.1. POSITIONING OF THE RESEARCH

The insertion of peripheral venous catheters is a daily practice in paediatric and neonatal wards. On average, more than 25 million peripheral venous catheters are inserted annually in France in all healthcare departments combined (1).

These catheters enable the administration of intravenous treatments (isotonic solutions, antibiotics, injectable drugs, etc.) as well as the collection of blood for analysis.

In departments such as paediatrics, these peripheral venous catheters can be difficult to insert due to the small venous capacity associated with the child's age. The difficulty increases when the child is afraid of needles or has had bad experiences, as anxiety activates the sympathetic nervous system, causing local peripheral vasoconstriction (2). Maintaining peripheral venous access (PVA) over time is also difficult due to children's mobility. In fact, 5% of peripheral venous catheters are accidentally removed in children (3).

For all these reasons and in accordance with HAS recommendations, there is no maximum duration for maintaining PIVCs in children (4) and nursing supervision is very important.

The routine use of peripheral venous catheters exposes children to iatrogenic risks such as severe skin damage. Approximately three-quarters of children hospitalised in paediatric wards are fitted with a peripheral or central venous catheter, with a rate of adverse events associated with care reaching up to 80%. However, this rate remains difficult to determine due to variations in the definition of a complication (5).

In 35% of cases, PIVCs are removed due to complications: infiltration (extravasation) 14.4%, occlusion 13.4%, signs of thrombophlebitis 7%, suspected infection 0.3%, wounds and injuries at the puncture site 0.2% (6).

Registered nurses, thanks to their experience and skills, play a fundamental role in the maintenance of peripheral venous catheters. Observation of puncture sites and monitoring of the complications mentioned above are well established in nursing practice.

For several years, we have observed skin changes such as redness and bedsores at the junction of the catheter and the peripheral venous line extender when removing peripheral venous catheters in our paediatric department. This junction between the catheter and the extension tube

is more prominent and is pressed against the skin by the occlusive dressing used to maintain the PIV. Regardless of the type of equipment used and the brand, this junction is always present. These pressure sores, which can cause pain and scarring on a child's skin, are difficult for a nurse to detect (before removing the PIVC) because they are located under the medical device and the fixation device.

In addition, the specific nature of paediatrics can make pressure sores difficult to detect. One of the main reasons for this is the difficulty of communicating with children about pain and discomfort.

A pressure ulcer is an ischaemic lesion caused by compression of soft tissue between a hard surface and a bony prominence (7). This prolonged compression causes tissue ischaemia. There are many risk factors for pressure ulcers, which are well described by the EPUAP (European Pressure Ulcer Advisory Panel) and the NPUAP (National Pressure Ulcer Advisory Panel) in their abbreviated reference guide (8).

These include intrinsic factors such as the child's age (level of activity and mobility, skin maturity), nutritional status, peripheral perfusion disorders, certain acute or chronic serious illnesses, and treatments.

Other factors, known as extrinsic or mechanical factors, such as pressure, friction, shear and maceration, are also known to cause pressure ulcers.

In our case, the pressure sores observed at the junction of the catheter and the peripheral venous line extender are mainly related to these extrinsic factors. These are referred to as iatrogenic pressure sores.

Numerous articles mention the fact that children fitted with medical devices are at risk of pressure ulcers. A separate section is devoted to them in the NPUAP's reference guide on the prevention and treatment of pressure ulcers (8).

It also specifies that pressure ulcers associated with medical devices are less studied in children than in adults.

To assess the risk of pressure ulcers in adults, there is a reference assessment scale, the Braden Q scale. This scale is also recommended for children to assess the risk of pressure ulcers related to medical devices. (9)

In a 2017 study, 8% of hospitalised children developed pressure ulcers, 2% of which were related to immobility and 6% to medical devices. (9)

In a 2013 article in the Paediatric Journal (10), various medical devices responsible for pressure ulcers are listed, such as intubation tubes, drains, orthopaedic splints, nasogastric tubes, oxygenation systems and intravenous catheters. Clinicians have identified that MDs positioned in contact with the skin can lead to the development of pressure ulcers. Although the aetiology of

pressure ulcers related to immobility and those related to MDs is different, the mechanism of wound formation is similar.

Few articles specifically discuss pressure ulcers associated with VVP.

These pressure ulcers associated with medical devices are not without consequences for children. In addition to skin damage, there is also psychological trauma related to the care and pain caused by the bedsores, which can make future treatment difficult (10).

An international classification system for pressure ulcer stages was established in 1998 by the National Pressure Ulcer Advisory Panel (8). This scale, which was initially validated on an adult population, is perfectly applicable to the classification of pressure ulcers in children.

Paediatric nurses use it systematically when removing catheters to assess the stage of the pressure ulcer. The pressure ulcers observed in our department and linked to the junction between the catheter and the extension tube are mainly stage I pressure ulcers.

In order to limit the occurrence of these pressure ulcers, specific recommendations are described by the NPUAP (8). These primarily concern the selection and assembly of the medical device. The device must be examined and selected within the institution so that the pressure and shear forces cause as little damage as possible. It must be used correctly in accordance with the manufacturer's specifications.

In addition, the skin and medical device must be inspected at least twice a day.

It is also recommended to keep the skin under the medical devices clean and dry and to use prophylactic dressings to reduce pressure at the skin-device interface.

As soon as medically possible, all medical devices that are a potential source of pressure sores should be removed.

In the Paediatrics Department at CHD Vendée, we try to follow these recommendations as closely as possible.

The equipment is selected by the pharmacy and the medical devices team.

Nurses are trained in pressure ulcer monitoring and ensure that VVP is monitored each time they visit, i.e. more than twice a day. Skin monitoring at the junction is limited because the catheter is held in place by a sterile occlusive dressing that cannot be changed at each monitoring session due to the risk of infection. In addition, the child's lack of cooperation and mobility can make care difficult. PIVCs in children are considered by nurses to be valuable medical devices for the child's recovery.

Following the observation of skin lesions at the catheter-extender junction in the department, a protocol for peripheral venous catheter placement was developed by the team and validated by the hygiene department of the CHD Vendée hospital. It stipulates the placement of a sterile compress cut to size under the hard parts of the medical device (at the catheter/extension junction) covered with a sterile transparent adhesive dressing. The choice of sterile compress is based on the fact that this type of dressing is readily available (a pack of sterile compresses is required for skin disinfection before catheter insertion) and inexpensive. The nurse must cut the compress in advance with sterile scissors to protect the area of contact between the skin and the medical device.

This practice was also recommended at the Pédiadol congress (11). To our knowledge, it is not widely used. We are only aware of practices in the paediatric intensive care unit at Trousseau Hospital, where a compress or thick hydrocolloid dressing is placed under the catheter and under hard areas to prevent pressure sores associated with medical devices. (12)

The application of these prophylactic dressings when inserting a PIVC is not taught to future healthcare professionals during their training at the Institute for the Training of Healthcare Professionals.

The latest SF2H recommendations from May 2019(13) on the placement and maintenance of peripheral venous catheters provide detailed information on infection prevention, but there are no recommendations on pressure ulcer prevention.

To date, no study has been published on this practice, which, if proven effective, would deserve to be more widely disseminated.

We therefore wish to conduct a controlled, randomised study to evaluate the benefits of compresses in the prevention of pressure ulcers associated with peripheral venous catheters.

This single-centre study will be a pilot study that will provide data that can then be used to consider a larger multicentre study if the compress proves to be an effective and safe tool in the prevention of pressure ulcers.

1.2. *BENEFITS AND RISKS FOR RESEARCH PARTICIPANTS*

1.2.1. *Benefits*

1.2.1.1. *Individual benefit*

If the hypothesis proves correct, participating in this study will enable patients in the "PIVC with compress" arm to reduce their risk of developing pressure ulcer-type skin lesions.

Pain and skin damage caused by pressure on this junction can be reduced. This practice would make it easier for children to accept treatment and limit the trauma of infusion.

Patients included in the "VP without compress" arm will receive standard care in other departments and hospitals.

1.2.1.2. *Collective benefit*

A collective benefit can be envisaged in terms of harmonising practices within different departments and hospitals. Better prevention of pressure sores associated with the placement and maintenance of VVP would enable compliance with NPUAP recommendations, namely to minimise the risk of pressure sores associated with medical devices. It would also reduce sources of pain.

1.2.2. *Risks*

1.2.2.1. *Individual risk*

The placement of VVP exposes patients to a risk related to the presence of medical devices:

- The risk of pressure ulcers exists in both groups;
- A minor risk of infection cannot be ruled out due to the presence of a dressing if it is soiled. Multiple daily monitoring by caregivers greatly minimises this risk.

1.2.2.2. *Collective risk*

Placing a compress under the catheter device does not present any collective risk except for an additional cost (sterile compress and scissors).

1.2.3. Benefit/risk balance

The research manager classifies this research as **minimally risky and minimally restrictive interventional research**, since:

- ✓ All procedures are performed in the usual manner and are defined in the decree of 12 April 2018 issued by the Ministry.

In fact, VVP placement is performed several times a day by registered nurses in the Paediatrics Department of the CHD Vendée hospital in La Roche-sur-Yon.

Furthermore, there are no recommendations regarding the choice of type of pressure ulcer prevention under medical devices.

The research does not focus on techniques or strategies that are either innovative or obsolete.

All patient care will be identical to usual practice. In particular, the discharge date will be decided by the doctor in charge of the patient, independently of the study, but will be recorded in the patient's file and the research CRF.

Consequently, the specific implementation procedures in the research represent negligible constraints for the person participating in the research. (Article R 1121-3 of the Public Health Code (CSP), Decree No. 2006-477 of 26 April 2006)

The research manager shall therefore submit, prior to any implementation of the research, for a favourable opinion and confirmation of the research's eligibility, the study protocol to the Committee for the Protection of Persons in accordance with Article L 1121-1 of the Public Health Code (CSP) as resulting from Laws No. 2004-806 of 9 August 2004 and No. 2006-450 of 18 April 2006 relating to public health policy.

Bibliographical references are listed in section 8 of the document.

2. OBJECTIVES AND ASSESSMENT CRITERIA

2.1. *OBJECTIVE AND MAIN ASSESSMENT CRITERION*

2.1.1. Primary objective

Compare the incidence of pressure sores during standard fixation versus fixation with a compress at the junction between the catheter and the extension tube in a paediatric population.

2.1.2. Primary assessment criterion

The primary endpoint is the occurrence of pressure ulcers of grade ≥ 1 on the NPUAP scale at the catheter/extender junction. The assessment will be carried out blind by a childcare assistant from the department.

2.2. *SECONDARY OBJECTIVES AND EVALUATION CRITERIA*

2.2.1. Secondary objective(s)

- Compare the severity of pressure ulcers at the catheter/tube junction.
- Compare the duration of peripheral venous catheter retention between the two groups.
- Compare the rate of nosocomial infections related to peripheral venous catheters between the two groups.

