2.2.2. Secondary evaluation criteria

- The severity of pressure ulcers will be assessed using the NPUAP scale

- The duration of catheter retention will be calculated between the time the catheter is inserted and the time it is removed.

- The presence of a nosocomial infection related to the peripheral venous catheter.

This will be defined by a peripheral venous catheter culture $>10^3$ CFU/ml, if the peripheral venous catheter is sent for culture due to suspected infection and in the absence of antibiotic treatment. In the presence of antibiotic treatment, it will be defined by the presence of pus and/or regression of infectious signs within 48 hours of removal of the peripheral venous catheter.

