4. DESIGN AND CONDUCT OF THE STUDY

4.1. STUDY SCHEDULE

- Recruitment period: 48 months
- Duration of patient participation in the study: until catheter removal.

a) Inclusion

Information and verbal consent regarding participation in the study will be obtained from the minor patient. Consent will be signed by the person(s) with parental authority (see 7.6.1: special case of the presence of only one parent).

This will be done once the medical prescription for peripheral venous access has been issued, the inclusion and exclusion criteria have been verified, and before randomisation.

The patient will be:

- either in the paediatric emergency department;
- or already hospitalised in paediatrics;

A table tracking patients to whom the study has been proposed will be kept up to date, noting the reasons for non-inclusion and refusals to participate.

b) Randomisation

Once consent to participate has been obtained, randomisation will be carried out via the computerised data base (eCRF):

- VVP placement without compress group: reference strategy group.
- VVP placement with compress group: alternative strategy group.

The peripheral venous line will then be placed according to the group designated by randomisation.

Details of the procedure for each arm are described in 4.4.

c) Follow-up

In both groups, catheter management and maintenance will be carried out by the nursing team responsible for the patient in the paediatric ward in accordance with current institutional procedures (see Appendices 1 and 2, catheter placement protocol with and without compress).

Data will be collected at the time of PPV removal. The peripheral line placed is valuable. In practice, the lines are maintained until the end of treatment unless there is redness and/or discharge at the puncture site.

When the catheter is removed, the nurse in charge of the patient removes the crepe bandage, the compress if there is one, and the catheter.

A childcare assistant from the department who has not been caring for the patient will then be called to assess the condition of the skin and report on the appearance and grade of any bedsores. The nurse will also note the presence or absence of signs of infection according to the Maddox scale. If the index is greater than 3, the paediatrician will prescribe that the catheter be sent for culture.

The microbiological analysis will be carried out by the clinical research biology team at the CHD Vendée.

d) Study design

[figure not shown]

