5.2. STATISTICS

Responsible for statistical analysis:

[name]
Vendée Departmental Hospital Centre
Clinical Research Unit
[contact]

Software

The analyses will be performed using R software version 3.5.1

5.2.1. Description of planned statistical methods, including the schedule for planned interim analyses

All variables will be described globally and by group. The description will include the numbers and percentages of modalities for qualitative variables and the minimum, maximum, mean, standard deviation and median for quantitative variables.

Primary endpoint

The primary endpoint is defined as the presence of a pressure ulcer at the junction of the catheter with the extension tube or peripheral venous line tubing. The assessment will be performed upon catheter removal and blinded by a nursing assistant from the department.

The percentage of patients will be presented with a 95% confidence interval in the two groups and will be compared using a Chi-square test.

In a second step, the two groups will be compared using logistic regression to take into account the duration of catheter retention.

Secondary criteria

The severity of pressure ulcers will be described between the two groups. At each stage of the NPUAP scale, the number and percentage of patients will be presented. A Mann-Whitney test will be applied to compare the two groups.

The average duration of catheter retention will be described for the two groups with a 95% confidence interval. It will be compared using a Student's t-test.

The number of patients with nosocomial infection will be described in the two groups. No statistical test will be performed.

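### The infection objective promises a between-group comparison, but the plan gives only counts without intervals, and at plausible infection rates 360 children cannot support a conclusion that the compress is safe

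*Combined protocol and SAP*

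**What the plan says.** Section 2.2.1 lists as a secondary objective: "Compare the rate of nosocomial infections related to peripheral venous catheters between the two groups". Section 2.2.2 defines the event in two ways. A positive catheter culture counts "if the peripheral venous catheter is sent for culture due to suspected infection and in the absence of antibiotic treatment". Under antibiotics the definition is clinical and rests on pus, or on signs that recede within 48 hours after the line is taken out.

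The analysis in section 5.2.1 reads: "The number of patients with nosocomial infection will be described in the two groups. No statistical test will be performed". No interval is mentioned for infection, although the same section plans 95% confidence intervals for the primary endpoint and for catheter duration.

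Section 1.1 closes by saying that the pilot data can be used to consider a larger multicentre study "if the compress proves to be an effective and safe tool in the prevention of pressure ulcers". No criterion for safe is given there or in section 5.2. Section 1.2.2.1 names a minor infection risk from a soiled dressing. Section 6 says that adverse events need not be reported to the sponsor.

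The only infection frequency in the document is in section 1.1, among the reasons for removal in a cited cohort: "In 35% of cases, PIVCs are removed due to complications", of which "suspected infection 0.3%, wounds and injuries at the puncture site 0.2" (both per cent).

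Section 4.1 adds an observation at removal in both groups: "The nurse will also note the presence or absence of signs of infection according to the Maddox scale". An index above 3 leads to culture. The score is not a listed endpoint and has no named analysis.

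**The concern.** The objective and its analysis do not match. The objective asks for a comparison of rates. The analysis gives two counts and nothing that expresses how uncertain the difference between them is.

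This matters because infection is the planned outcome that bears most directly on harm, and safety is one of the two conditions attached to a larger study. If events are as rare as the cited figure suggests, the likely result is 0 against 0, or 0 against 1. Without intervals and without a stated limit on interpretation, such a table could pass for evidence that the compress does not raise infection risk. In fact it would say little either way.

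**Working it through.** **The plan's own figure.** The total of 346 in section 5.2.2 concerns the pressure-ulcer endpoint only. Arm rates are not given. With assumed rates of 55% and 40%, two-sided 5% alpha, 80% power and the pooled-variance formula:

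n per arm = [1.96 × √(2 × 0.475 × 0.525) + 0.842 × √(0.55 × 0.45 + 0.40 × 0.60)]² / 0.15² = 172.8, rounded up to 173, so 346 in total.

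The figure reproduces, but it has no bearing on infection. No calculation supports the infection objective.

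**Inputs for the infection check**
- 360 randomised (section 5.2.2), 1:1 (section 5.2.8), so 180 per arm.
- Infection rate 0.3% (section 1.1), used as an order of magnitude. Its denominator is all catheters: 14.4 + 13.4 + 7 + 0.3 + 0.2 = 35.3, which agrees with the stated 35%.
- Assumed range 0.1% to 1%, because the trial's own rate is unknown.

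**Expected events in both arms together**

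| Assumed rate | Expected cases (360 × rate) | Chance of none, (1 − rate)^360 | Chance of 6 or more |
|---|---|---|---|
| 0.1% | 0.36 | 70% | below 0.1% |
| 0.3% | 1.08 | 34% | 0.1% |
| 1% | 3.6 | 3% | 15% |

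At 0.3% the chance of none or one is 71%.

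**What the likely results would show**
- 0 of 180 in the compress arm: exact two-sided 95% upper limit = 1 − 0.025^(1/180) = 2.03%. This is 2.03 / 0.3 = 6.8 times the cited rate.
- 0 against 0: Newcombe 95% interval for the difference, −2.1 to +2.1 points.
- 1 of 180 against 0 of 180: the difference is 0.56 points. The Wilson limits are 0.10% to 3.08% and 0% to 2.09%. Newcombe lower limit = 0.56 − √[(0.56 − 0.10)² + 2.09²] = −1.6 points. Newcombe upper limit = 0.56 + √[(3.08 − 0.56)² + 0²] = +3.1 points.

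**Would adding a test help?** No. With 180 per arm and no cases in one arm, Fisher's exact test needs 6 cases in the other (p = 0.030; 5 against 0 gives p = 0.061). The column for 6 or more cases shows how seldom that total would even arise if both arms share the assumed rate. Exact power is 3.4% for 0.3% against 1.5%, and 32% for 0.3% against 3%. Detecting a doubling from 0.3% with 80% power would need about 15,600 children in total.

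**The case against.** The strongest reply is that the plan already treats infection as descriptive. It declines a test, so the power figures do not count against anything it intends to do, and no section states that a low count will be taken as proof of safety. That is fair. What remains is the verb in section 2.2.1, the missing intervals and the undefined condition in section 1.1.

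A reader might infer more than the documents support:

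- **That the trial will proceed to a multicentre study if the compress looks safe.** Section 1.1 says only that such a study may be considered, and there is no go/no-go rule. A larger study is also where a rare infection could be better measured.
- **That the trial's infections must be rarer than 0.3% because they need confirmation.** Section 2.2.2 has a clinical route under antibiotics, and section 4.1 has signs noted at every removal. The cited figure counts catheters removed because of suspected infection in another cohort. The trial's rate could be lower or higher, so one case is not a forecast.
- **That infection is the only outcome bearing on harm.** Section 1.2.2.1 lists the infection risk under placement of the line in general. Catheter duration is also compared, and could reflect early removal for local signs.
- **That the Maddox score is a ready-made safety endpoint.** The contents of Appendix 3 are not shown, so its entry in the eCRF is unconfirmed. If it is collected, section 5.2.1 already has every variable described by group. It is noted by staff who know the allocation, and no expected frequency is given. The 7% for thrombophlebitis signs in section 1.1 is a reason for removal, not the frequency of any Maddox sign. Even if 7% applied, the half-width for the difference would be 1.96 × √(2 × 0.07 × 0.93 / 180) = 5.3 points, and power for 7% against 14% would be 52% (Fisher) to 58%.

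**Conclusion.** The concern holds in a limited form. The objective to compare infection rates has no analysis that answers it, and the safety condition has no criterion. At an assumed 0.3%, about one case is expected in 360 children, with a 34% chance of none. Over 0.1% to 1%, 0.4 to 3.6 cases are expected. The likely results leave an upper limit of 2.0% in the compress arm (0 of 180), or a difference anywhere from about −1.6 to +3.1 points (1 against 0), so a several-fold rise cannot be excluded.

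This rests on 180 evaluable children per arm and on the assumed range of rates. It does not depend on 0.3% being right: at an assumed 2%, with 360 × 0.02 = 7.2 cases, the comparison would still be imprecise. The primary endpoint and its sample size are not affected. Nor do the documents show that the sponsor plans an unsupported safety claim; they leave room for one, and a small change would close it.

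**What to change.** - **Section 2.2.1:** change the infection objective from *compare* to *describe*.
- **Section 5.2.1:** report infections as counts with exact 95% confidence intervals per arm, and a 95% confidence interval for the between-arm difference (Newcombe, for example). Keep the decision not to test.
- **Sections 5.2.1 and 1.1:** state that no conclusion of absence of harm will be drawn from few or no events, and that *safe*, as a condition for considering a larger study, is to be read with that limit.
- **Maddox score:** confirm whether it is captured in the eCRF. If so, report it by arm with the between-arm difference and 95% confidence interval, as a supportive outcome only, noting that it is recorded unblinded. Do not make it the criterion for *safe*.

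The cost is some rewording and one extra table. The safety claim becomes weaker, which is what the expected number of events allows.
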